**D. RESEARCH DESIGN AND METHODS****D1. Study subjects and overview of experimental protocol**

PCOS subjects will be recruited from the Endocrinology Clinics of the University of Chicago. All will be at least 18 but less than 40 yr of age. All recruited subjects will be obese (BMI of at least 30 kg/m^2). This BMI criterion is met in 80.7% of PCOS subjects in our database, as shown in Preliminary Studies. A schematic of the overall study design for Specific Aims 1 – 3 is presented in **Figure D1-1 below**. A summary grid of all testing procedures planned is shown in **Table D1**. Sample size calculations and statistical considerations follow and are presented in **Section D3**, below.

*All subjects enrolled in this project will have a confirmed diagnosis of PCOS. A diagnosis of PCOS will require: 1) the presence of oligo/amenorrhea; 2) hyperandrogenemia, defined by a supranormal plasma free testosterone level (> 10 pg/ml); 3) hyperandrogenism, as evidenced by infertility, hirsutism, acne, or androgenetic alopecia; and 4) exclusion of nonclassic 21-hydroxylase deficiency congenital adrenal*

*Specific Aim 1*

**Figure D1-1. Schematic of overall study design for Specific Aims 1 - 3.**

hyperplasia, Cushing syndrome, hypothyroidism, or significant elevations in serum prolactin. Thus, all subjects will meet the so-called NIH criteria for PCOS (113) as well as the Rotterdam criteria for PCOS (114). For at least 2 months before the study, all subjects must not take steroid preparations (including oral contraceptives), medications known to alter insulin secretion and/or action, or medications known to influence sleep. All studies will be conducted in the follicular phase of the menstrual cycle (days 1 – 7) or after 2 or months of amenorrhea. A negative pregnancy test will be required prior to all testing procedures. Subjects who are known to be diabetic will be excluded; those who prove to be diabetic on screening will not continue in subsequent protocols. Subjects with hypertension (systolic > 140 mmHg and/or diastolic > 90 mmHg) will be included only if well-controlled on stable medication with either ACE inhibitors or diuretics. Subjects on beta-blockers will be excluded as these drugs affect both insulin sensitivity and sleep. Subjects must have regular life styles (no shift work, no travel across time zones within 4 weeks of study), and habitual bedtimes. Other exclusion criteria will be: habitual alcohol use of more than 2 drinks per day and excessive caffeine intake of more than 300 mg per day.

Table D1. Summary Grid of Tests by Specific Aim.	SPECIFIC AIM 1		SPECIFIC AIM 2		SPECIFIC AIM 3
	Obese PCOS OSA Negative	Obese PCOS OSA Positive	Obese PCOS OSA Positive		Obese PCOS OSA Positive
			Depot Leuprolide	Depot Leuprolide	
			Estrogen plus Placebo	Progesterone plus Placebo	CPAP
SAMPLE SIZE	23	23	20	20	20
Oral glucose tolerance test (OGTT)	2	2	2	2	2
Frequently sampled IVGTT (fsIVGTT)	2	2	2	2	1
Androgen levels (total, free T, et al.)	1	1	2	2	2
Estradiol, Estrone, Progesterone	1	1	2	2	2
Gonadotropins (LH, FSH)	2	2	2	2	2
Metabolomics profile (blood, urine)	2	2	2	2	2
24 hr hormonal profiles (including Cortisol and Catecholamines)	2	2	2	2	1
Plasma catecholamines	2	2	2	2	2
Abdominal MRI, Bioimpedance	2	2	2	2	2
Adipose tissue biopsy	2	2	2	2	2
Serum for adiponectin	2	2	2	2	2
Sleep and Activity Assessment	2	2	2	2	2
Sleep questionnaires	2	2	2	2	2
Wrist activity monitoring	2	2	2	2	2
Multiple sleep latency test (MSLT)	2	2	2	2	2
Sleep recording/Polysomnography	1	1	1	1	1
Wake EEG/Neurobehav. assessments	2	2	2	2	2
Daytime blood pressure recording	2	2	2	2	2
24 hr heart rate monitoring	2	2	2	2	2
GnRH agonist test with steroid intermediates	2	2	2	2	2

## D2. Screening and Specific Aim 1 Procedures

46 subjects will need to be enrolled in Specific Aim 1 in order to ensure a sample size of 20 in the group of PCOS women without OSA; this figure of 46 subjects is based on an estimated 55% prevalence of OSA among PCOS women as shown in Preliminary Studies. This calculation accounts for the effects of expected dropouts from the study. The primary outcome measures for this Aim are the differences in progesterone and estrogen concentrations between groups.

[figure not shown]
Following an initial phone screening, eligible subjects will be admitted to the GCRC in the early evening and will undergo the following screening process as described in Figure D2-1, below.

**N.B. THE SCREENING PROTOCOL DETAILED BELOW WILL PERTAIN TO ALL SPECIFIC AIMS. BASED UPON THE RESULTS OF THIS SCREENING, SUBJECTS WILL BE CLASSIFIED AS EITHER OSA NEGATIVE, IN WHICH CASE THE**

EVALUATION IS COMPLETED, OR WILL BE CLASSIFIED AS **OSA POSITIVE**. OSA POSITIVE SUBJECTS WILL THEN BE GIVEN THE OPTION TO ENTER INTO THE PROTOCOLS DETAILED IN SPECIFIC AIM 2 OR SPECIFIC AIM 3. SUBJECTS WILL BE INFORMED THAT IF THEY CHOOSE TO CONTINUE INTO AIM 2 OR AIM 3, THEY WILL BE RANDOMLY ASSIGNED USING A RANDOMIZATION SCHEDULE PREPARED BY THE GCRC BIOSTATISTICIAN, DR. [name]. SUBJECTS RANDOMLY ASSIGNED TO SPECIFIC AIM 2 WILL ALSO BE INFORMED THAT FURTHER RANDOMIZATION WILL OCCUR TO ONE OF TWO TREATMENTS, AS DETAILED BELOW.

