#### C4. There is a 5-6 fold increase in risk for OSA in PCOS

We have obtained a polysomnogram and metabolic measures in 49 women with PCOS and 22 women without PCOS (Controls). Among the 22 Controls, 4 (18%) met criteria for OSA (using the most common AHI criterion of  $\geq 5$  events/hr of sleep). In contrast, 27 (55%) of 49 women with PCOS had OSA. The unadjusted odds ratio of 5.5 for OSA in PCOS is highly significant ( $p=0.006$ ; 95% CI 1.6 – 18.7). Even after adjustment for age and BMI, the odds ratio remains highly significant at 5.5 ( $p=0.009$ ; 95% CI 1.5 – 20.6). Within group comparisons are shown in Tables C4-1 and C4-2. The magnitude of metabolic abnormalities is greater in the presence of OSA as well. Control women with OSA had significantly higher diastolic blood pressure levels; 2hr glucose levels were also higher, but significance was lost after correction for multiple comparisons. PCOS women with OSA were significantly higher in age relative to those without OSA, but it is important to note that these women are only in their second and third decades of life. In addition, BMI and waist circumference were significantly higher in PCOS women with compared to those without OSA. As was the case in controls, 2hr glucose levels were also significantly higher, but significance was lost after correction for multiple comparisons. Finally, those with OSA had higher fasting insulin concentrations as well as higher levels of fasting triglycerides. Thus, in women with or without PCOS, the presence of OSA is associated with more profound metabolic abnormalities.

[figure not shown]
[figure not shown]
Table C4-1.

	Controls Without OSA	Controls With OSA	P- value*
n	18 (82%)	4 (18%)	
Age (yr)	29.9 $\pm$ 1.2	34.4 $\pm$ 1.9	0.123
BMI (kg/m  )	35.3 $\pm$ 1.5	40.7 $\pm$ 4.3	0.160
Waist Circ (cm)	97.1 $\pm$ 3.6	110.4 $\pm$ 8.6	0.123
Systolic BP (mmHg)	114.1 $\pm$ 3.3	134.0 $\pm$ 6.2	0.012
Diastolic BP (mmHg)	67.6 $\pm$ 1.9	80.3 $\pm$ 3.8	0.007*
Fasting glucose (mg/dl)	88.3 $\pm$ 2.2	94.9 $\pm$ 5.2	0.228
2hr glucose (mg/dl)	111.6 $\pm$ 6.5	151.6 $\pm$ 29.1	0.046
Fasting Insulin (pmol/L)	11.6 $\pm$ 1.7	11.8 $\pm$ 3.2	0.972
HOMA	0.4 $\pm$ 0.1	0.5 $\pm$ 0.1	0.877
A1C (%)	5.4 $\pm$ 0.1	5.8 $\pm$ 0.3	0.067
Cholesterol (mg/dl)	163.5 $\pm$ 6.4	172.0 $\pm$ 8.6	0.553
HDL (mg/dl)	54.8 $\pm$ 3.2	49.0 $\pm$ 5.3	0.417
Triglycerides (mg/dl)	76.2 $\pm$ 13.0	86.5 $\pm$ 9.2	0.712
LDL (mg/dl)	93.7 $\pm$ 6.5	105.5 $\pm$ 9.3	0.416

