### **Screening and Specific Aim 1 Procedures, cont'd.**

**Figure D2-1. Schematic of Screening Visit. Clock time is shown along horizontal axis.**

Subjects will receive instructions on the logs/scales and practice the psychomotor vigilance test (PVT) to be used in the study. Subjects will also complete screening questionnaires including the Pittsburgh Sleep Quality Index, Berlin Questionnaire, Epworth Sleepiness Scale, Center for Epidemiologic Studies-Depression (CES-D) scale, Functional Outcome of Sleep Questionnaire (FOSQ), and the Beck Scale. An overnight full polysomnography will be performed to differentiate the subjects with from those without OSA.

For all protocols in this SCOR application the presence of OSA will be defined by an apnea-hypopnea index (AHI) of greater than 15 events per hour sleep (AHI > 15); the absence of OSA will require an AHI of less than 5 events per hour sleep (AHI < 5). This criterion is consistent with current standards and ensures that subjects with periodic limb movement disorder (PLM arousal index > 1) are excluded from study.

On the day following the full polysomnography, a 2 hr OGTT, a complete history and physical examination, routine laboratory tests (CBC, electrolytes, renal, liver function tests) and an EKG will be performed. This screening visit will also serve to familiarize the subject with the study environment and the experimental procedures.

[figure not shown]
Once the Screening Visit has been completed if the subject is deemed eligible to continue, they will be instructed on completing one week of continuous wrist actigraphy at home; subjects will be asked to maintain a standardized schedule of bedtimes and mealtimes designed in accordance with their usual habits. They will be asked not to deviate from this schedule by more than 30 minutes. During this pre-study period, subjects will also be asked to fill out a daily log of sleep and meal times. Subjects who have shown poor compliance will be given the option to repeat the week of ambulatory recordings. If compliance remains poor, subjects will be excluded from further study.

After the screening visit and completion of the ambulatory recordings, the subsequent experimental procedures depicted in Figure D2-2 and described below will occur.

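### Aim 1's enrolment of 46 does not contain the dropout allowance claimed for it: on the stated 55% OSA prevalence it yields about 20.7 women without OSA, room for only 3.4% loss

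*Combined protocol and SAP*

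**What the plan says.** Section D2 (Screening and Specific Aim 1 Procedures) sets Aim 1 enrolment at 46 "in order to ensure a sample size of 20 in the group of PCOS women without OSA". It gives the basis ("this figure of 46 subjects is based on an estimated 55% prevalence of OSA among PCOS women as shown in Preliminary Studies") and then adds: "This calculation accounts for the effects of expected dropouts from the study". Section D3, Statistical Considerations, repeats the 46 and the 55% without mentioning dropouts, and bases power on 20 per group.

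The other figures that bear on this are:

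- **Source of the 55%.** Section C4 reports that "27 (55%) of 49 women with PCOS had OSA", using AHI ≥ 5 as the criterion.
- **Definitions for the trial.** Section D2 (continued) and the polysomnography text in D5 require AHI > 15 for OSA and AHI < 5 for its absence. The screening text in D2 nevertheless names only two outcomes: "SUBJECTS WILL BE CLASSIFIED AS EITHER OSA NEGATIVE" or OSA positive.
- **Group sizes.** Table D1 lists 23 OSA-negative and 23 OSA-positive women for Aim 1.
- **Retention.** Section D4, under Aim 1, cites retention above 90% in similar studies. No dropout rate is stated anywhere.

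**The concern.** Three claims are attached to one number: that 46 comes from the 55% prevalence, that it makes 20 women without OSA certain, and that it already absorbs dropouts. If the prevalence alone uses up nearly all of the 46, nothing is left for dropouts and the third claim is unsupported. Table D1's equal split also looks like the product of a different calculation.

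At stake is whether the smaller group in the Aim 1 comparison of progesterone and estrogen will reach the size on which its power statement rests, and whether a reader can tell from the plan how large either group should be.

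**Working it through.** **Inputs.** Target 20 without OSA (D2); enrolment 46 (D2, D3); share without OSA 1 − 0.55 = 0.45 (C4: 22/49 = 0.449); retention 90% as the floor of the D4 figure; effect 0.89 SD, two-sided alpha 0.05 (D3). The 0.45 is the right share for this purpose, because the complement of AHI ≥ 5 is AHI < 5, the trial's own definition of no OSA.

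**1. Power statement.** For 20 v 20 at 0.89 SD, power is 80% by the normal approximation and 78% by the noncentral t. The plan's figure of about 80% is fair.

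**2. Reproducing 46.**

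- Prevalence only: 20 / 0.45 = 44.4, so 45. Close to 46, but with no dropout allowance.
- Prevalence and 10% loss: 20 / (0.45 × 0.90) = 49.4, so 50.
- Prevalence and 5% loss: 20 / (0.45 × 0.95) = 46.8, so 47.
- Equal groups and 10% loss, no prevalence: 20 / 0.90 = 22.2, so 23 per group; 2 × 23 = 46. This matches both the total and Table D1.

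**3. What 46 yields on the stated basis.** This counts all screened women, including those with AHI 5–15, within the 46.

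- Expected without OSA: 46 × 0.45 = 20.7.
- Loss that still leaves 20: 1 − 20/20.7 = 3.4%, so retention of 96.6% is needed.

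| Retention | Expected without OSA | Chance of at least 20 (binomial, n = 46) |
|---|---|---|
| 100% | 20.7 | 0.64 |
| 95% | 19.7 | 0.52 |
| 90% | 18.6 | 0.39 |

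**4. The other way of counting.** Suppose women with AHI 5–15 are screen failures outside the 46. The share without OSA among the 46 is then 0.45 / (0.45 + s), where s is the share of screened women with AHI > 15. The documents do not give s; 25%, 35% and 45% are assumed here.

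| s (assumed) | Without OSA, before loss | After 10% loss | Enrolment for 20 after 10% loss: 20(0.45 + s)/(0.45 × 0.90) |
|---|---|---|---|
| 25% | 46 × 0.45/0.70 = 29.6 | 26.6 | 34.6, so 35 |
| 35% | 46 × 0.45/0.80 = 25.9 | 23.3 | 39.5, so 40 |
| 45% | 46 × 0.45/0.90 = 23.0 | 20.7 | 44.4, so 45 |

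The target is met in expectation, but the required enrolment now depends on s and cannot be obtained from the 55% alone.

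**5. Effect of the shortfall on power** (noncentral t, 0.89 SD). For 18.6 v 22.8, where 22.8 is 46 × 0.55 × 0.90, power is 79%. For 18.6 v 20 it is 77%. Both are close to the 78% at 20 v 20.

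**The case against.** The strongest reply is that the shortfall depends on how women with AHI 5–15 are counted. They are excluded from both groups, and D2 lets only women judged eligible continue after screening, so treating them as screen failures outside the 46 is a natural reading. After 10% loss the expected number without OSA is then about 21 to 27 over the assumed range, and the chance of at least 20 is 64% to 98%. This stands, and it makes the 18.6 and the 0.39 conditional. It does not rescue the stated justification, because on that reading 46 does not follow from the 55%. Figure D1-1 is not reproduced in the text available and may show the flow, but the written basis in D2 and D3 would still need to agree with it.

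A reader might also infer that Table D1's 23/23 contradicts a 25.3/20.7 split implied by the prevalence. The documents do not support that. The 25.3 counts women with AHI ≥ 5, whereas the OSA-positive group requires AHI > 15, and an assumed AHI > 15 share of 45% with the middle band outside the 46 gives exactly 23 v 23. What can be said is that the 23 per group is not reconciled with the stated basis.

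Two further replies have some force. The retention figure is a floor, so 96.6% or better is compatible with it; but no such rate is stated, and the word *ensure* fails even with no loss. Sizing on an expected number is also ordinary practice, and even 50 women would reach 20 only 58% of the time at 90% retention. That argues for describing 20 as expected.

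**Conclusion.** The justification is wrong as written, and the consequence is minor. On the basis that D2 states, 46 women give an expected 20.7 without OSA, tolerate 3.4% loss, and leave 18.6 at 90% retention; 20 is neither certain nor protected against dropouts. The 46 can be matched by prevalence with almost no dropout allowance, or by equal groups with a dropout allowance and no prevalence, but not by prevalence with 10% loss. The yields assume that women with AHI 5–15 are counted within the 46.

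A reader might infer that Aim 1 is underpowered. That is not shown. Dropout alone leaves power at 77–79%. A larger loss would need few women with AHI > 15, women with AHI 5–15 using places in the 46, and no use of the additionally enrolled OSA-positive women. The documents establish none of these.

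Nor do they require the additionally enrolled women to join the Aim 1 comparison. The section on methods for Aims 2 and 3 distinguishes them from the women studied in Aim 1, and the total of 60 refers to women randomized to those later aims. Including them would be an optional design choice, separate from this correction.

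**What to change.** In this order, because the second step depends on the first:

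1. State in D2 and D3 whether the 46 are counted before or after women with AHI 5–15 are excluded.
2. On that basis, give the expected number without OSA before and after a stated dropout rate. If women with AHI 5–15 are inside the 46, these are 20.7 and, at 10% loss, 18.6. If they are outside, state the assumed share with AHI > 15 and derive the number from it.
3. Replace *ensure* with *expected*, and correct the sentence on dropouts.
4. Reconcile the 46, the 20 per group and Table D1's 23 per group.

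Alternatively, if 20 women without OSA is to be a firm target, say that enrolment continues until 20 women with AHI < 5 have completed Aim 1, in place of a fixed 46. With women with AHI 5–15 counted as enrolled, that means about 50 in expectation at 10% loss, or 4 more than planned.

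The main correction costs only wording in the protocol and its statistical section. It requires no extra patients or tests.

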### **Screening and Specific Aim 1 Procedures, cont'd.**

**Figure D2-1. Schematic of Screening Visit. Clock time is shown along horizontal axis.**

Subjects will receive instructions on the logs/scales and practice the psychomotor vigilance test (PVT) to be used in the study. Subjects will also complete screening questionnaires including the Pittsburgh Sleep Quality Index, Berlin Questionnaire, Epworth Sleepiness Scale, Center for Epidemiologic Studies-Depression (CES-D) scale, Functional Outcome of Sleep Questionnaire (FOSQ), and the Beck Scale. An overnight full polysomnography will be performed to differentiate the subjects with from those without OSA.

For all protocols in this SCOR application the presence of OSA will be defined by an apnea-hypopnea index (AHI) of greater than 15 events per hour sleep (AHI > 15); the absence of OSA will require an AHI of less than 5 events per hour sleep (AHI < 5). This criterion is consistent with current standards and ensures that subjects with periodic limb movement disorder (PLM arousal index > 1) are excluded from study.

On the day following the full polysomnography, a 2 hr OGTT, a complete history and physical examination, routine laboratory tests (CBC, electrolytes, renal, liver function tests) and an EKG will be performed. This screening visit will also serve to familiarize the subject with the study environment and the experimental procedures.

[figure not shown]
Once the Screening Visit has been completed if the subject is deemed eligible to continue, they will be instructed on completing one week of continuous wrist actigraphy at home; subjects will be asked to maintain a standardized schedule of bedtimes and mealtimes designed in accordance with their usual habits. They will be asked not to deviate from this schedule by more than 30 minutes. During this pre-study period, subjects will also be asked to fill out a daily log of sleep and meal times. Subjects who have shown poor compliance will be given the option to repeat the week of ambulatory recordings. If compliance remains poor, subjects will be excluded from further study.

After the screening visit and completion of the ambulatory recordings, the subsequent experimental procedures depicted in Figure D2-2 and described below will occur.

The subjects will have an abdominal MRI exam at 4 pm to quantify visceral and subcutaneous fat. They will then be admitted to GCRC at 18:00 (day 1) and a standardized dinner will be provided at 19:00. The subjects will also review the PVT and questionnaires that will be used during the study. After a night of full polysomnography (day 2), 2 blood samples (12 cc for Metabolomics and 1 cc for detailed lipid profile) and a urine sample (5 cc for Metabolomics) will be obtained. This will be followed by the subcutaneous fat biopsy. The subjects will then receive a breakfast. At 9:45, 11:45, 13:45, 15:45 and 17:45, the subjects will perform the PVT and complete various questionnaires (sleepiness, vigor, mood, hunger and appetite) followed by a Multiple Sleep Latency Test (MSLT). A lunch will be provided around 14:30, depending on the MSLT duration. After the 17:45 MSLT, a bioimpedance will be obtained to measure body fat. A dinner

will be offered around 19:00 after these procedures. After a night of polysomnography (day 3), the subjects will undergo a frequently sampled intravenous glucose tolerance test (fsIVGTT) at approximately 09:00, depending on their usual bedtimes. Starting at 14:00, 24 hour blood sampling will be initiated, with intervals of every 15, 30 or 60 minutes for measurements of glucose, C-peptide, insulin, adiponectin, GH, cortisol, leptin, C-reactive protein (CRP, assayed only every 4 hours), estrogen, testosterone, progesterone, ghrelin and catecholamines (q60min) levels. Free fatty acids (FFA) will be obtained before and, 1 hour and 2 hours after each meal. FFA will also be obtained every hour during the night. Concomitant with the 24-hour blood sampling, during the waking period, saliva samples will be obtained every 30 minutes for free cortisol assay, and daytime systolic and diastolic blood pressures will be measured at 15-minute intervals.

**Figure D2-2. Experimental protocol after completion of ambulatory recordings**

[figure not shown]

Every 2 hours, the subjects will perform the PVT and complete the visual analog scales. Subjects will also have a recording of wake EEG brain activity and an EKG to assess their heart rate variability (HRV). Caloric intake will be controlled with carbohydrate-rich meals served at 14:00 for lunch, 19:00 for dinner, and 9:00 for breakfast, after a night of polysomnography. The subjects will be asked to eat each meal entirely within 20 minutes. Accelerometer-based assessments of activity will be obtained continuously during the entire study (Actical). At the end of the 24-hour blood sampling period (14:00 on day 4), the subject will receive a lunch.

**At 15:50, a GnRH agonist test will be performed, as depicted in FIGURE D2-3 below.**

At 15:50, a 15cc blood sample for LH, FSH, estradiol, estrone, total and free testosterone, progesterone, 17-hydroxyprogesterone, and androstenedione will be obtained. At 15:59, a 5 cc blood sample will be taken for LH and FSH. At 16:00, leuprolide acetate 10 µg/kg will be given as a single subcutaneous injection. At 16:30, 17:00 and 20:00, 5 cc samples will be obtained for LH and FSH. A 15 cc sample will be obtained for estradiol, estrone, total and free testosterone, progesterone, 17-hydroxyprogesterone, and androstenedione after 16, 20, 24 hours GnRHa administration, i.e. at 8:00, 12:00 and 16:00.

As depicted in Figure D1-1, it is at this point that subjects will have completed the Screening and Specific Aim 1 Procedures. Details of procedures for subjects randomized into Specific Aim 2 or Specific Aim 3 are provided below.

### D3. Detail of methods pertaining to Specific Aims 2 and 3

The PCOS women with OSA studied in Aim 1 plus additionally enrolled PCOS women with OSA (for a total of 60 subjects) will be randomized in a ratio of 2:1 to participate in Aim 2 (n=40) or Aim 3 (n=20). Block randomization will be performed using computer-generated random numbers. The primary outcomes measure for Aim 2 is the AHI difference pre- and post-interventions, as detail in Section D3; the primary outcomes measure for Aim 3 is the change in 24 hr cortisol concentration pre- vs post-CPAP

Subjects randomized to Specific Aim 2 will have suppression of endogenous LH secretion, and thus ovarian sex-steroid production, by administration of a single intramuscular dose (11.25 mg) of the GnRH agonist depot leuprolide. Leuprolide is a synthetic nonapeptide analog of naturally occurring gonadotropin-releasing hormone (GnRH). The analog possesses greater potency than the natural hormone. When the depot form of leuprolide is administered at a dose of 11.25 mg, there is prolonged (3 month) suppression of pituitary gonadotropin levels and ovarian steroid levels as documented in the literature (115) and exemplified in Preliminary Studies. Six-weeks after administration, subjects will return to the GCRC for repeated evaluation, identical to that conducted at Baseline under Specific Aim 1.

After this midpoint assessment, subjects will again enter into a randomized phase of the protocol. Subjects will be assigned to receive one of two treatment regimens in a randomized, double-blind, placebo controlled fashion, for a period of 6 weeks. Subjects will receive daily oral doses of either **2 mg micronized estradiol (Estrace®) plus placebo –OR– 200 mg micronized progesterone (Prometrium®) plus placebo.**

Rationale for preparation and dose of estrogen and progesterone. Natural estradiol is poorly absorbed in its native form and undergoes rapid metabolism in a first-pass effect through the liver. Thus, micronization (micronized estradiol) or acetylation (ethinyl estradiol) is required to achieve adequate blood hormone levels. Micronized estradiol is extremely well-absorbed and much of the compound is metabolized to estrone sulfate (65%) and estrone (15%). This “pool” of estrone and estrone sulfate then serves as the source of regenerated estradiol. At a dose of 2 mg per day, the steady-state levels of estradiol and estrone are typically 220 pmol/L and 68 pmol/L, respectively (116) and most closely recapitulate those seen in normal women in the midfollicular phase of the menstrual cycle (110). Because ethinyl estradiol is poorly converted to estrone, it will not be selected for use in these protocols. Micronized progesterone at a dose of 200 mg per day has been reported to result in attainment of serum progesterone concentrations typically seen in the late follicular/early luteal phase of the cycle (data provided by manufacturer).

Subjects randomized to Specific Aim 3 will be treated with nasal CPAP for a period of 6 weeks. Compliance will be documented based upon results provided by a microchip sensor that detects not only if the unit is powered on, but also if the mask is being worn by the subject. These data cannot be altered by the individual and there is no access to this microsensor by the user. The subjects who have OSA will undergo one night of CPAP titration study at the end of the baseline assessment. After 6 wks of home CPAP, the experimental study outline above will be repeated with CPAP use at night. Subjects whose average nightly CPAP use is > 5 hr will be considered compliant.

